6.2.5 Sponsor Responsibility for Reporting Adverse Events

All Adverse Events will be reported to regulatory authorities, IRB/IECs and investigators in accordance with all applicable global laws and regulations.

6.3 Procedures for filing complaints

Patients will be able to communicate directly with the doctor / researcher or with the research nurses of the study (by phone or by visiting the centre) for any grievance, complaint or any clarification they need, in relation to the study. All patients are going to receive a card with all the necessary contact details for the participating doctors and research nurses. The same information is going to be available on the consent form.

Complaints can also be submitted in person or anonymously to the Chief Executive Officer of the Bank of Cyprus Oncology Centre (BOCOC), [name]. Finally, complaints can be posted in a complaints box located in the main entrance of the building at the BOCOC.

7.0 STATISTICAL ANALYSIS PLAN

7.1 Statistical Analysis Plan Summary

The study employs a one stage phase II Fleming's design using irPFS at 1 year as primary endpoint.

Using response hypotheses of $H_0 < 12\%$ and $H_a > 25\%$ i.e. that the irPFS at 1 year for the maintenance Pembrolizumab arm is 25%, compared to 12% in the normal chemotherapy maintenance arm, with a significance level (i.e., the probability of rejecting H_0 when it is true) $\alpha=0.05$ and the power (i.e. the probability of deciding the regimen is active) is 0.8 when true response rate is 25%, 48 patients are required to be entered into this study.

7.2 Statistical Analysis Plan

Comparator data regarding patients' outcomes receiving maintenance therapy can be obtained from the Pemetrexed continuation and Erlotinib switch maintenance studies.

The best available data for maintenance treatment of non-squamous NSCLC patients come from the continuation Pemetrexed trial (Pas Ares¹⁶). This trial enrolled good performance status patients (PS 0-1), with non-squamous histology, who did not progress after 4 cycles of Pemetrexed / Cisplatin, and continued Pemetrexed chemotherapy, resulting in a 1-year PFS of 18.6%, whilst in the placebo arm the 1 year PFS was 5%.

For the squamous patients, the best available data come from the switch maintenance Erlotinib trial²¹ (SATURN), given that Erlotinib is the only agent approved for maintenance treatment in patients with squamous cancers. The 1-year PFS for the erlotinib arm is slightly above placebo, around 6%.

Hence for the comparator arm by using:

- data from the Pemetrexed continuation study for non squamous histology: 1-year PFS of 18% for non squamous on Pemetrexed maintenance,
- data from the erlotinib arm in the SATURN trial for patients with squamous histology and estimating 1-year PFS of 6% for squamous patients
- whilst assuming a ratio of 1:1 adenocarcinomas to squamous,
- provides us a weighted average of 12% of 1-year PFS

Assume irPFS at 1 year for the maintenance Pembrolizumab arm to be 25%, compared to 12% in the normal chemotherapy maintenance arm.

Sample size for Fleming one stage Phase II trials

Probability of Type I Error (α) = 0.05

Power ($1 - \beta$) = 0.8

Lower proportion for rejection (p_0) = 0.12

Higher proportion for acceptance (p_n) = 0.25

Sample size required = 48

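### Section 7.2 quotes 18.6% for pemetrexed but averages 18%; its own figures put the null near 12.3%, a small shift in the drug's favour, and no success count is fixed for the 48 patients

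*Combined protocol and SAP*

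**What the plan says.** Section 7.2 derives the null rate from two historical maintenance trials. It describes the pemetrexed continuation trial in non-squamous disease as "resulting in a 1-year PFS of 18.6%, whilst in the placebo arm the 1 year PFS was 5" per cent. In the list that builds the comparator, the same arm appears as "1-year PFS of 18% for non squamous on Pemetrexed maintenance". The erlotinib figure for squamous disease is given only approximately, at about 6%. The two are averaged 1:1 to reach 12%.

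That 12% becomes the design null, "Lower proportion for rejection (p_0) = 0.12", and is also the benchmark in Sections 1.1 and 7.1. With an alternative of 25%, "Probability of Type I Error (α) = 0.05" and power 0.8, Section 7.1 concludes that "48 patients are required to be entered into this study". Neither 7.1 nor 7.2 says how many of the 48 must be progression-free at 1 year for the null to be rejected.

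**The concern.** One arm of one trial has two values a few lines apart, and the one used in the calculation is the lower. It is not conventional rounding: 18.6% to the nearest whole per cent is 19%. The trial has a single arm, so this null is the only comparator. A lower null makes success easier to declare and makes the required sample size look smaller. The plan also has almost no slack, since the formula gives 47.82 against the 48 planned. Even a small change in the null therefore affects the claim of 80% power at alpha 0.05.

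**Working it through.** **Inputs (Sections 7.1 and 7.2).** Null p0 = 0.12; alternative p1 = 0.25; alpha = 0.05; power = 0.80; n = 48; pemetrexed 18.6% as reported and 18% as used; erlotinib about 6%; weights 1:1. The SAP does not say whether the test is one- or two-sided. The hypotheses are directional, and only the one-sided form gives 48 (two-sided gives 60), so one-sided is assumed.

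**Step 1: reproduce the plan's 48.** One-stage Fleming design, normal approximation:

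n = [(1.645·√(p0(1−p0)) + 0.842·√(p1(1−p1))) / (p1−p0)]²

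At p0 = 0.12: n = [(1.645·√0.1056 + 0.842·√0.1875) / 0.13]² = 47.82, so 48. The formula power at n = 48 is Φ{[(p1−p0)·√n − 1.645·√(p0(1−p0))] / √(p1(1−p1))} = 80.1%. The stated sample size is reproduced.

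**Step 2: carry 18.6% through.**
- As used: (18 + 6)/2 = 12.0%.
- As reported: (18.6 + 6)/2 = 12.3%.

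**Step 3: same formula at p0 = 0.123.** n = [(1.645·√0.107871 + 0.842·√0.1875) / 0.127]² = 50.74, so 51. Formula power at n = 48 is 78.4%.

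**Step 4: cut-off implied by the formula at n = 48.** n·p0 + 1.645·√(n·p0(1−p0)):
- p0 = 0.12: 5.76 + 3.70 = 9.46.
- p0 = 0.123: 5.90 + 3.74 = 9.65.

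Both mean at least 10 of 48.

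**Step 5: exact binomial error rates at n = 48.**

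| Success rule | Alpha at 12% | Alpha at 12.3% | Power at 25% |
|---|---|---|---|
| ≥10 of 48 | 5.6% | 6.4% | 79.5% |
| ≥11 of 48 | 2.5% | 2.9% | 68.4% |

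Reading across, the change in null moves only alpha. Reading down, neither rule gives alpha of at most 0.05 together with power of at least 0.80, even at 12%. A lower cut-off only raises alpha further, and a higher one only lowers power further. The smallest n that meets both exactly is 53 (≥11) at 12% and 58 (≥12) at 12.3%.

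**The case against.** The strongest reply is that 12.3% claims more precision than the inputs carry. The erlotinib figure is an estimate. With 18.6% kept, a value of 5.4% would give (18.6 + 5.4)/2 = 12.0% exactly, and 6.5% would give 12.55%. The plan works in whole per cents, and 12.3% to the nearest per cent is 12%. The 1:1 mix is itself an assumption. All of this stands, and it limits how much weight the 0.3 points can bear. It does not explain why the precisely reported input was cut down while the approximate one was entered as it was.

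A reader might infer that the sample size is wrong, or that 48 patients do not give 80% power. The documents do not support that. For the null they state, 48 is correct and formula power is 80.1%. The 78.4% appears only once the null is moved to 12.3%, and it is 1.6 points below target. In exact terms the truncation costs no power, because the rule stays at ≥10 of 48.

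A reader might also attribute the 68.4% power to the truncation. It comes from choosing ≥11 rather than ≥10, and it is 68.4% at a 12% null as well.

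**Conclusion.** The inconsistency is real and runs in the drug's favour, but its effect is small. Using the SAP's own 18.6%, approximate 6% and 1:1 weights, the null is about 12.3%. The formula then asks for 51 rather than 48, formula power at 48 is 78.4% rather than 80.1%, and the exact type I error of the implied ≥10 rule is 6.4% rather than 5.6%. This is an unexplained truncation to correct or justify, not an invalid sample size.

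A related gap does not depend on the truncation. At n = 48 the stated pair of alpha 0.05 and power 0.8 holds only by normal approximation, and no critical count is prespecified. An outcome of exactly 10 of 48 would pass under one reasonable rule and fail under the other.

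These figures assume a one-sided test, 48 evaluable patients and a binary endpoint at 1 year.

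**What to change.** Keep n = 48 and change the text.

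1. In Section 7.2, enter 18.6% in the average and set p0 = 12.3%, with 7.1 and the 12% in 1.1 brought into line. Otherwise, state why 18% is the right input.
2. If p0 becomes 12.3%, restate the formula power at 48 as about 78%. If 12% is justified and kept, the formula power of 80.1% stands.
3. Say that the test is one-sided, and prespecify one critical count with its exact properties. At p0 = 12.3% the choices are:
   - ≥11 of 48: alpha 2.9%, power 68%. This holds alpha at 0.05.
   - ≥10 of 48: alpha 6.4%, power 79.5%, both stated openly in place of the nominal 0.05 and 0.8.

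   If 12% is kept, the corresponding alphas are 2.5% and 5.6%, with the same powers.

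The cost is text only, with no extra patients or assessments. The downside is that either the stated power or the stated alpha becomes less favourable. The drop is modest with ≥10 but about 12 points of power (80% to 68%) with ≥11, so the choice should be made deliberately and before the outcome data are reviewed.

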1.0 TRIAL DESIGN

1.1 Trial Design

Single arm one stage Phase II study: post 4-6 cycles platinum doublet chemotherapy for patients with metastatic Non Small Cell Lung Cancer (NSCLC) offering Pembrolizumab as maintenance therapy to non-progressors with primary endpoint: Immune Related Progression Free Survival (irPFS) at 1 year. Aim to show that this is at least 25% (compared to an expected 12% 1 year PFS based on the Pemetrexed and Erlotinib maintenance trials).

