1.2 Trial Diagram

2.0 OBJECTIVE(S) & HYPOTHESIS(ES)

2.1 Primary Objective(s) & Hypothesis(es)

Objective: The main objective of this trial is to provide efficacy data for Pembrolizumab as maintenance therapy after first line therapy for NSCLC. Especially relevant would be evidence of a higher percentage of patients being progression free at 1 year (primary endpoint), increased response rates, increased Progression free and Overall Survival (OS) compared to the results from other chemotherapy maintenance studies.

Hypothesis: Pembrolizumab can provide superior outcomes in terms of disease control (% of patients Progression Free at 1 year using Immune Related response criteria) compared to other maintenance treatments (specifically pemetrexed continuation maintenance for non-squamous NSCLC and erlotinib switch maintenance for squamous NSCLC).

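### The 12% null for 1-year irPFS rests on an unsupported 1:1 histology mix, and no planned analysis relates that benchmark to the patients enrolled

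*Combined protocol and SAP*

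**What the plan says.** Section 7.2 builds the comparator rate from two historical trials. For non-squamous disease it uses "1-year PFS of 18% for non squamous on Pemetrexed maintenance", although the same section first reports the pemetrexed trial as "resulting in a 1-year PFS of 18.6" per cent. For squamous disease it says "The 1-year PFS for the erlotinib arm is slightly above placebo, around 6" per cent, and carries this forward as "estimating 1-year PFS of 6% for squamous patients". The two are combined "whilst assuming a ratio of 1:1 adenocarcinomas to squamous", which gives 12%. No source or site data are offered for the ratio.

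Section 1.1 presents the target as "Aim to show that this is at least 25" per cent, "compared to an expected 12% 1 year PFS based on the Pemetrexed and Erlotinib maintenance trials". Section 2.1 states the hypothesis as superiority over other maintenance treatments, "specifically pemetrexed continuation maintenance for non-squamous NSCLC and erlotinib switch maintenance for squamous NSCLC".

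Section 4.1.1 admits any metastatic NSCLC that has not progressed on a first-line platinum doublet. Sections 4.1.2 and 4.1.3 set no histology quota, and Section 4.4 marks stratification as not applicable. Sections 7.1 and 7.2 contain the design and sample size only. The one endpoint split by histology, in Section 3.2.3.1, is best overall response and disease control, not 1-year irPFS.

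**The concern.** The two component rates differ threefold, so the benchmark that matches the trial's patients depends on how many have each histology. It is 6% plus 12% times the non-squamous share, and it equals 12% only at 1:1. The plan neither controls the mix nor says how the result will be read if the mix differs.

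If most patients are non-squamous, passing against 12% could be taken as superiority to the named comparators when it partly reflects who enrolled. If most are squamous, 12% is a higher bar than those comparators set, and a narrow failure could undersell the drug. Because the direction cannot be known in advance, the rule should be fixed before outcomes are seen. A re-weighting chosen afterwards would be open to selection.

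**Working it through.** **Inputs.** From Section 7.2: 18% (18.6% as first reported) and 6%; p0 = 0.12, p1 = 0.25, alpha 0.05, power 0.80, N = 48. The plan states neither the sidedness of alpha nor a cut-off. The enrolled mix is not in the documents, so every mix below is an assumption.

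**1. The plan's own figures reproduce.**
- Null: 0.5 × 18% + 0.5 × 6% = 12%.
- Sample size by the Fleming normal approximation, one-sided: n = [(1.645 × √(0.12 × 0.88) + 0.842 × √(0.25 × 0.75)) / 0.13]² = [(0.5345 + 0.3644) / 0.13]² = 47.8, so 48.
- Implied cut-off: 48 × 0.12 + 1.645 × √(48 × 0.12 × 0.88) = 9.46, so at least 10 of 48.

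Exact binomial properties at a flat 12% null and 25% alternative:

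| Rule | Exact alpha | Power |
|---|---|---|
| ≥10/48 | 5.6% | 79.5% |
| ≥11/48 | 2.5% | 68.4% |
| ≥12/48 | 1.0% | 55.5% |

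The rule ≥11 is the first with exact alpha at or below 5%. The rule ≥12 applies only if the 25% in Section 1.1 is meant as the observed rate (12/48 = 25%).

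**2. Benchmark and pass probability by enrolled mix.** Suppose each histology group has exactly its comparator's rate. The number progression-free at 1 year is then Bin(n_ns, 0.18) + Bin(n_sq, 0.06), with n_ns + n_sq = 48. The exact upper tail of this sum is the chance that a drug merely equal to its comparators passes. Values at 18.6%/6% are in brackets.

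| Non-squamous : squamous | Benchmark at 18%/6% | ≥10/48 | ≥11/48 | ≥12/48 |
|---|---|---|---|---|
| 16:32 | 10.0% | 1.7% (1.9%) | 0.6% (0.7%) | 0.2% (0.2%) |
| 24:24 | 12.0% | 5.3% (6.1%) | 2.2% (2.6%) | 0.9% (1.0%) |
| 30:18 | 13.5% | 10.2% (11.7%) | 4.9% (5.8%) | 2.2% (2.6%) |
| 33:15 | 14.25% | 13.4% (15.4%) | 6.9% (8.1%) | 3.2% (3.9%) |

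For example, the 33:15 benchmark is 6% + 12% × 33/48 = 14.25%. That mix matches the only histology counts in the documents, from a first-line trial described in Section 3.1.1: (847 + 153) / 1473 = 67.9% non-squamous. They illustrate a mix other than 1:1 and do not predict this trial's.

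**3. Separating the mix from the cut-off.** Part of the excess under ≥10 is not due to the mix, since that rule already has exact alpha 5.6% at a flat 12%. Under ≥11 and the plan's rates, the chance stays below 5% up to 30:18.

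**4. Chance variation around a true 1:1 source.** Each patient then has probability 0.5 × 0.18 + 0.5 × 0.06 = 0.12, so the total is Bin(48, 0.12). The average error is unchanged: 5.6% (≥10) or 2.5% (≥11). If the source were 60:40 (assumed), the probability is 0.132 and the averages are 9.4% and 4.5%.

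**5. Uncertainty in the comparator rates.** At 33:15, assumed rates of 16%/5% give 7.0%, 3.1% and 1.3% under the three rules. Assumed rates of 20%/8% give 24.3%, 14.3% and 7.7%. This spread is as large as the effect of the mix.

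**The case against.** The strongest reply is that nothing in the primary test is wrong. The 1:1 ratio is declared as an assumption, and 12% and N = 48 follow from the inputs. Sections 1.1 and 7.1 turn the hypothesis into one pooled comparison of 25% with 12%, and no separate claim by histology is planned. All of this stands.

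It also stands that the larger percentages need both the ≥10 rule and a mix well away from 1:1, and that under ≥12 the concern is small. Re-weighting cannot repair the historical comparison either. The squamous rate is only approximate, the pemetrexed trial enrolled PS 0-1 while this one admits ECOG 0-2 (Section 4.1.2), and historical PFS is set against irPFS, which needs confirmed progression (Section 10.3).

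A reader might infer more: that the type I error is inflated, that the 12% test should be replaced, or that enrolment will be mostly non-squamous. The documents support none of these. The error against 12% does not depend on histology labels, and the enrolled mix is not given.

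What the reply leaves open is the link from result to hypothesis. Section 2.1 names a comparator for each histology, and no planned analysis shows whether 12% represents those comparators in the patients studied.

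**Conclusion.** The concern holds as a gap in interpretation, not as an error in the primary test. The 12% benchmark matches the named comparators only at an unsupported 1:1 mix. Across the illustrative mixes from 16:32 to 33:15, the chance that a drug equal to its comparators passes runs from 1.7% to 13.4% under ≥10, and from 0.6% to 6.9% under ≥11. The bias is anti-conservative when more than half are non-squamous and conservative when fewer are.

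These figures rest on the plan's 18% and 6% being right, on 48 patients with a 1-year outcome, and on cut-offs inferred because the plan states none. A cheap supportive analysis is worth adding. Replacing the primary test is not warranted.

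**What to change.** Keep the 12% primary test and N = 48. Pre-specify one supportive analysis in the same patients:

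- Report the enrolled histology mix and the benchmark it implies, 6% + 12% × non-squamous share, with 18.6% in place of 18% as a sensitivity.
- Give the exact one-sided tail probability of the observed count under Bin(n_ns, 0.18) + Bin(n_sq, 0.06), at the counts actually analysed. Section 4.9 allows no replacement, so these may total fewer than 48.
- Report 1-year irPFS with exact confidence intervals for each histology.
- Before outcomes are analysed, fix how mixed or unclassified histology is assigned. Section 7.2 weights by adenocarcinoma although its 18% is for all non-squamous disease.
- Show a range of comparator rates, for example 16%/5% and 20%/8% (both assumed).

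State the reading in advance. If the result is not shown to exceed the mix-weighted benchmark, confine the conclusion to being above a fixed 12%. Judge this by the exact tail: 10/48 is 20.8%, already numerically above even the all-non-squamous benchmark of 18%, so the point estimate cannot discriminate. If the result does exceed the benchmark, call it supportive and no more, for the reasons given under the objection.

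The cost is one SAP paragraph and one further exact test. No patients or new data are needed, because histology is already required for the secondary endpoint in Section 3.2.3.1, and primary power is unchanged. The downside is a possibly less favourable reading if enrolment is mostly non-squamous.

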3.2.3 Rationale for Endpoints

3.2.3.1 Efficacy Endpoints

Primary endpoint: percentage of patients that have not progressed at 1 year using immune related radiological criteria (see section 11.3). The 1 year timing relates to the time from trial enrolment and initiation of pembrolizumab as maintenance therapy. This is the most clinically relevant endpoint in a maintenance study. Prolongation of disease control is a very worthwhile endpoint, towards the realization of the goal to obtain long term disease control for patients with metastatic NSCLC, similar to the results seen with checkpoint inhibition for patients with melanoma. The timing of assessment at 1 year is based on the durable nature of responses seen with Pembrolizumab so far, suggesting that at 1 year there is going to be a large difference in disease progression between patients on Pembrolizumab compared to the historical data from the maintenance studies.

Secondary Endpoints: These would include

- Response rates (RECIST)
- Response Rates with immune related Response Criteria (irRC)
- Radiological Progression Free Survival (PFS) using RECIST criteria
- Immune-related PFS using irRC: irPFS is the progression free survival (PFS) measured applying immune related radiological criteria. PFS (RECIST) at 6 months and 1 year from initiation of Pembrolizumab.
- Overall survival
- 1, 2 and 3 year OS rate.
- Best overall response rate and disease control rate using both RECIST and irRC in patients with squamous and non-squamous NSCLC and
- Immune-related toxicities (IRAEs)

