10.2 Common Terminology Criteria for Adverse Events V4.0 (CTCAE)

The descriptions and grading scales found in the revised NCI Common Terminology Criteria for Adverse Events (CTCAE) version 4.0 will be utilized for adverse event reporting. (<http://ctep.cancer.gov/reporting/ctc.html>)

10.3 Response Evaluation Criteria in Solid Tumors (RECIST) 1.1 Criteria for Evaluating Response in Solid Tumors

Both RECIST version 1.1³⁴ and immune related Response Criteria³⁵ (irRC) will be used in this study for assessment of tumor response. While either CT or MRI may be utilized, as per RECIST 1.1, CT is the preferred imaging technique in this study.

The use of irRC is to correct for the possibility of pseudo-progression / deal with the altered patterns of response seen with ipilimumab and potentially other immunotherapies [Wolchok JD al³⁵, table 8].

The decision to discontinue treatment is going to be based on irRC assessment. The irRC assessment considers the patient's "total tumour burden" and requires confirmation of suspected disease progression with a subsequent CT scan, four weeks later.

Table 8. Immune related response rates:

Immune-related complete response	Complete resolution of all measurable and nonmeasurable lesions, with no new lesions. Complete response must be confirmed by a second, consecutive assessment at least four weeks later.
Immune-related partial response	A decrease in the total tumor burden of 50 percent or more compared to baseline, which must be confirmed by a second, consecutive assessment at least four weeks later. This category allows for the inclusion of progression of some lesions or the appearance of new lesions as long as the total tumor burden meets the response criterion.
Immune-related stable disease	Not meeting the criteria for either a partial or complete response or for progressive disease.
Immune-related progressive disease	An increase in tumor burden of 25 percent or more relative to the minimum recorded tumor burden. This must be confirmed by a second, consecutive assessment no less than four weeks after the initial documentation of an increase in tumor

11.0 REFERENCES:

2. M. Reck, S. Popat, N. Reinmuth, et al. Metastatic Non Small Cell Lung Cancer: ESMO Clinical Guidelines *Ann Oncol* (2014) 25 (suppl 3): iii27-iii39.

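### One-year irPFS is tested against a 12% benchmark labelled as PFS, and the RECIST PFS already planned is given no role in reading the result

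*Combined protocol and SAP*

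**What the plan says.** Section 7.1 names the tested quantity: "The study employs a one stage phase II Fleming's design using irPFS at 1 year as primary endpoint". Section 7.2 builds the null from 18% for non-squamous disease (pemetrexed continuation) and 6% for squamous disease (erlotinib switch), both labelled 1-year PFS, in a 1:1 mix that "provides us a weighted average of 12% of 1-year PFS". It then sets the irPFS target against that figure: "Assume irPFS at 1 year for the maintenance Pembrolizumab arm to be 25%, compared to 12% in the normal chemotherapy maintenance arm". Section 1.1 makes the same pairing, with a 25% irPFS aim "compared to an expected 12% 1 year PFS based on the Pemetrexed and Erlotinib maintenance trials".

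Elsewhere the protocol separates the two measures. Section 3.2.3.1 lists RECIST PFS and irPFS as distinct endpoints, explains that "irPFS is the progression free survival (PFS) measured applying immune related radiological criteria", and also plans "PFS (RECIST) at 6 months and 1 year from initiation of Pembrolizumab". Section 10.3 gives the purpose of the immune-related criteria: "The use of irRC is to correct for the possibility of pseudo-progression". It says they judge total tumour burden and require a confirming scan. The partial-response row of Table 8 adds: "This category allows for the inclusion of progression of some lesions or the appearance of new lesions", provided the total burden still meets the response criterion.

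Section 2.1 states the hypothesis as superiority over pemetrexed and erlotinib maintenance, using immune-related criteria. It also states a general aim of longer PFS than in other maintenance studies, without naming criteria or method.

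**The concern.** The benchmark and the endpoint carry different labels. On the protocol's own description, irRC can leave a patient classed as progression-free whom conventional criteria would count as progressed. This can happen when a later scan refutes the progression, when it is never confirmed, or when it is absorbed into total burden.

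Timing may add to this. Scans fall every 9 weeks in year 1 (section 6.1.2.6), so those nearest 1 year are at weeks 45 and 54. A confirming scan four weeks after week 45 falls at week 49, before 1 year. But Table 8 sets four weeks only as a minimum, so the week-54 scan would also qualify, and no section says whether irPD is dated to the scan that raised the suspicion or to the one that confirmed it.

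The trial is single-arm, so nothing in the design separates a criteria effect from a drug effect. What is at stake is the superiority statement over pemetrexed and erlotinib maintenance, which would rest on a figure measured, as far as the label shows, in a different way.

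**Working it through.** **Inputs (section 7.2).** p0 = 0.12, pA = 0.25, alpha = 0.05, power = 0.80, N = 48. Sidedness and the success cut-off are not stated.

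**Benchmark.** 0.5 × 18% + 0.5 × 6% = 12%. The arithmetic is right; every component is labelled 1-year PFS.

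**Sample size.** Fleming one-stage, normal approximation:

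n = [(1.645 × √(0.12 × 0.88) + 0.842 × √(0.25 × 0.75)) / 0.13]² = 47.8, so 48.

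The plan's figure reproduces with one-sided alpha. Two-sided alpha gives 59.3, so 60, which does not match.

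**Cut-off (inferred).** 48 × 0.12 + 1.645 × √(48 × 0.12 × 0.88) = 5.76 + 3.70 = 9.46, so success at ≥10/48. Exact alpha is then 0.056 and power 0.795. If exact alpha must not exceed 0.05, the cut-off is ≥11/48, with alpha 0.025 and power 0.684. Both are shown below.

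**Illustration 1: a drug no better than the benchmark by RECIST.** Assume true 1-year RECIST PFS of 12%, and that irRC leaves on average k more of 48 patients progression-free, so the irPFS rate is 0.12 + k/48. Assume also that every patient free of progression on RECIST is free on irRC (nesting). Exact binomial, n = 48:

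| k (assumed) | irPFS rate | irPFS passes, ≥10 | irPFS passes, ≥11 |
|---|---|---|---|
| 0 | 12.0% | 5.6% | 2.5% |
| 1 | 14.1% | 13.0% | 6.7% |
| 2 | 16.2% | 24.0% | 14.2% |
| 3 | 18.3% | 37.7% | 25.1% |

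The 5.6% at k = 0 comes from the cut-off, not from the criteria.

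Under nesting, the chance that irPFS reaches the cut-off while RECIST PFS does not is each row minus the k = 0 row. For k = 1, 2, 3 this is 7.4%, 18.4%, 32.1% at ≥10, and 4.2%, 11.7%, 22.6% at ≥11. These are the trials in which a RECIST figure beside the primary result would alert the reader.

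**Illustration 2: what the addition costs an active drug.** Assume true irPFS of 25% and RECIST PFS k/48 lower, again nested:

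| k (assumed) | RECIST reaches ≥10 | irPFS does, RECIST does not, ≥10 | RECIST reaches ≥11 | irPFS does, RECIST does not, ≥11 |
|---|---|---|---|---|
| 0 | 79.5% | 0% | 68.4% | 0% |
| 1 | 68.8% | 10.7% | 55.6% | 12.8% |
| 2 | 55.7% | 23.8% | 41.6% | 26.7% |
| 3 | 41.2% | 38.3% | 28.1% | 40.3% |

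**The case against.** The strongest reply is that no conversion may be needed. Section 10.3 justifies irRC by response patterns seen with immunotherapy, and the comparators are chemotherapy and a kinase inhibitor. If pseudo-progression belongs to the test drug, the comparator rate could be about 12% on either scale, and extra patients free of progression on irRC could reflect real disease control. This stands as a possibility. The plan does not make the argument, however, and total-burden scoring and confirmation could also move a comparator's rate.

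Four further points stand.

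- The documents do not say which criteria the source trials used; that they were conventional is inferred from the PFS label.
- k and the nesting are assumptions. Against 5.76 expected RECIST progression-free patients, k = 1, 2, 3 are relative increases of 17%, 35% and 52%, which are not small. The new-lesion wording comes from the partial-response row of Table 8 and does not define progression.
- RECIST PFS at 1 year is planned and section 2.1 already aims at better PFS than other maintenance studies, so the data and the intent exist. What is missing is a reference value, an interval and a place in the interpretation.
- Any single-arm historical comparison has other differences. Some may act the other way: this trial admits PS 0-2 (section 4.1.2), the pemetrexed trial PS 0-1 (section 7.2).

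A reader might go further and infer that irPFS is an invalid endpoint, or that the test's error rate is really 24%. The documents support neither. Against its null as written, an irPFS rate of 12%, the test has the exact error rates shown for k = 0; the larger figures depend on an assumed shift. Nor do the documents supply a better null. Raising it above 12% would need a conversion they do not contain.

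**Conclusion.** The plan's only specified test compares 1-year irPFS with a 12% figure labelled 1-year PFS, unconverted and without justification, while the protocol treats the measures as different. An irPFS result above 12% may therefore mix drug effect with a criteria effect, to which confirmation timing may contribute.

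The size is not known from the documents. On assumed shifts of 1 to 3 patients in 48, the chance that a drug at 12% by RECIST passes on irPFS rises from 5.6% to 13.0%-37.7% at ≥10/48, or from 2.5% to 6.7%-25.1% at ≥11/48. This rests on the inferred cut-offs, the assumed k and the reading of the source figures as conventional PFS; the probabilities of a split result also rest on nesting. Part of any irRC gain may be real benefit.

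The sample-size and averaging arithmetic is sound, and the choice of irPFS is not in question. The point concerns how a comparison with pemetrexed and erlotinib maintenance is supported and worded. It is a cheap improvement, not a flaw that undermines the trial.

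**What to change.** Keep 1-year irPFS as the primary endpoint, with its test and N = 48. In sections 7.1 and 7.2:

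- Prespecify 1-year RECIST 1.1 PFS with an exact confidence interval, set against the 12% benchmark, as a supporting analysis reported beside the primary result.
- State that the 12% is a conventional-PFS figure, after checking this against the source trials.
- State that if only irPFS exceeds 12%, the report will say so wherever it compares the result with pemetrexed or erlotinib maintenance.

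This takes a few sentences and uses the same scans, the same patients and an endpoint already listed. It adds no second pass/fail test and leaves the definition of irPFS events alone. It does not remove the other differences from the source trials.

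The downside is that a like-for-like superiority statement becomes harder to support. If irPFS is truly 25% and RECIST PFS is 1 to 3 patients in 48 lower, irPFS would reach the cut-off and RECIST PFS would not in 10.7%-38.3% of trials at ≥10/48, or 12.8%-40.3% at ≥11/48.
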